5.1 Concomitant Medication Therapy

Patients will be instructed to take Prednisone to prevent/alleviate any acute inflammation. The steroid should be taken:

20mg BID on the day of the cryotherapy procedure

20mg BID on the day after the procedure

20mg BID two days after the procedure

20mg AM and 10mg PM three days after the procedure

10mg AM and 10mg PM four days after the procedure

10mg five days after the procedure

5mg six days after the procedure

STUDY CALENDAR

	Pre-Cryotherapy	Cryotherapy	Week 1 ^H	Week 2 ^H	Week 3	Thoracotomy ^J	Month 6
Diagnosis	X						
Informed Consent	X						
Demographics	X						
Medical History	X						
Physical Exam ^G	X ^C						
Chest X-ray	X ^B	X	X	X			
CT scan of chest	X ^B				X ^I		X
PET scan	X ^A						X
MRI of brain	X ^D						
Pulmonary Function Tests (PFTs)	X ^D				X ^I		
EKG	X ^D						
CBC w/differential	X ^C						
Chem-7 ^F , alkaline phosphatase, SGOT, bilirubin	X ^C						
INR	X ^E						
Pregnancy test, urine or serum	X ^E						
Histology						X	

B: Must be performed within 42 days of cryotherapy

C: Must be within 6 weeks of cryotherapy

D: Must be within 12 weeks of cryotherapy

E: Must be within 1 week of cryotherapy

F: Chem-7 includes BUN, creatinine, glucose, and electrolytes

G: Physical exam to include heart, rate, blood pressure, respiratory rate, temperature and documentation of concurrent medication

H: +/- 2 days

I: 2-53 days following percutaneous cryotherapy; within 7 days of planned thoracotomy

J: Less than 12 weeks from percutaneous cryotherapy

6.0 ADVERSE EVENTS

Adverse event monitoring and reporting is a routine part of every clinical trial. The following list of adverse events and the characteristics of an observed adverse event will be expeditiously reported when the event occurs.

1. Pneumothorax - In the placement of cryoprobes, and after removal of the percutaneous probes, the patient may develop a pneumothorax in the treated area. This may be noted on a chest x-ray obtained following the percutaneous treatment. It may also be noted on subsequent chest x-rays. The patient may become short of breath. Only ~15% pneumothoraces have been reported after cryoablation of the lung³², usually only on large masses located centrally.
2. Hemothorax –One of the advantages of cryotherapy is the preservation of the blood vessel architecture. A hemothorax may be more likely, if a central lesion was being treated. Treatment of more peripheral lesions makes this unlikely. Subsequent chest x-ray or complete blood counts may be indicated. A significant hemothorax would require either percutaneous drainage with a catheter or the patient might have his/her thoracotomy performed sooner than three weeks after operation.
3. Hemoptysis - This would more likely occur with central lesions rather than with this protocol. However, when the probes are used for cryotherapy, a pulmonary vessel could be penetrated and hemoptysis might result. If this developed prior to cryoablation, the therapy would not be administered. If the hemoptysis was self-limited, CBC would be obtained as well as chest x-ray and CT scans to primarily ensure that the hemoptysis has not resulted in secondary areas of consolidation other than the treated area. If the hemoptysis is significant, the patient would require a bronchoscopy and possibly operation prior to the three-week interval after therapy.
4. Nerve Damage - If cryotherapy was in the area of the phrenic nerve, recurrent laryngeal nerve or in the area of the brachial plexus, it is possible that nerve damage could result. Brachial damage would be demonstrated by anesthesia of the extremity affected, or any weakness in the motor strength of the affected extremity. Phrenic nerve damage would be noted by elevated diaphragm on the treated side. Further evaluation of the phrenic injury could be performed with fluoroscopy to determine if the diaphragm was able to contract. Recurrent laryngeal nerve damage would present as hoarseness but would be unlikely since masses in this study would not be near the aorto-pulmonary window.

Any of these adverse events would be reported. In addition, any event that requires hospitalization, placement of a tube, or any interventions such as bronchoscopy or early operation, would then be reported as protocol-specific adverse events.

7.0 CORRELATIVE / SPECIAL STUDIES

We propose to correlate the patient's CT scan before the operation with the final pathology result.

Any changes that are noted on the CT scan in relation to the pathologic specimen may have predictive value. Imaging studies such as chest CT scan, or PET scan will be a requirement to ensure that no tumor remains after therapy. Since future patients who are not operative candidates will require imaging studies to determine the presence or absence of tumor following therapy, any prediction value of imaging studies will be very important.

The PET scans will be performed and interpreted by [name] [contact]) of Karmanos Cancer Center/Wayne State University, [name].

FDG(F-fluoro-deoxy-D-glucose)- is a radiolabelled glucose used in PET imaging that is transported into the cells. It is accumulated in neoplastic cells at a more rapid rate than normal tissue. Non-neoplastic disease such as granulomatous and inflammatory processes could also accumulate PDG and give false results, there a histologic analysis of cryotreated tissue (both neoplastic and inflammatory processes) needs to be done to evaluate the cryotherapy effect on the neoplasm.

FDG uptake will be measured as Standard Uptake Value (SUV). Standard Uptake Value is calculated by the following formula: $SUV = \text{radioactivity concentration in ROI (Region of Interest)} (\mu\text{Ci/ml}) \text{ divided by injected dose } (\mu\text{Ci})/\text{body weight (kg)}$. The SUV mean will be measured over the whole Region of Interest (ROI). The SUV max will be measured as the uptake in the hottest pixels in the same ROI.

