2.0 OBJECTIVES

The primary objective of the study is to evaluate the histologic result of treating primary lung cancer or solitary metastatic lung cancer after PTC.

The secondary objective is to provide a qualitative assessment of the histology from the ablation and tumor margins, comparing histologic observations with imaging enhancement patterns by computed tomography (CT) before and after PTC. Post-cryotherapy, pre-surgical CT scan dimensions and characteristics (e.g., central necrosis and healing rim) will be qualitatively compared to similar areas of the surgical specimen. In addition, histology samples from anterior, posterior, superior, inferior, medial and lateral areas of the resected tumor will be compared to enhancement zones of the ablation margin for any residual cancer.

A tertiary objective is long term follow up for clinical outcome and overall survival.

A total of ten evaluable patients qualifying in either Cohort A or Cohort B will be included.

Cohort A. Patients who have been diagnosed with Stage I primary peripheral lung cancer less than 3.0 cm in average diameter without prior radiation or chemotherapy.

Cohort B. Patients with metastatic solitary or multiple (≤ 3) peripheral lung lesions less than 3.0 cm in average diameter which have not been treated with radiation or chemotherapy since the new metastatic lesion appeared.

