5.0 TREATMENT PLAN

All patients who have been diagnosed with primary Stage I lung cancer or limited metastatic disease, confirmed by percutaneous transthoracic needle biopsy or transbronchial biopsy will also have a CT scan of the chest, MRI of the brain and a PET scan. All patients will have no evidence of cerebral disease, no evidence of metastatic disease by the PET scan or the CT scan. This will include no evidence of satellite lesions on the CT scan of the chest, no mediastinal lymph nodes greater than 1.5 cm. There will be no hepatic or adrenal masses noted. MRI of the brain will not demonstrate evidence of metastatic disease. PET scan may show only significant uptake in the primary lung lesion. There will be no areas that have SUV of greater than 2.5 in any location other than a primary lesion considered under control in the metastatic subgroup. The lesion on the lung CT scan must be in the peripheral third of the lung.

The patients with metastatic lung cancer will have a solitary or limited number (≤ 3) of lesions less than 3.0 cm diameter. They will have prescreening MRI of the brain, which demonstrates no evidence of disease, the chest CT scan and PET scan will demonstrate no evidence of other metastatic disease and control of the primary tumor. Patients will then undergo treatment with percutaneous cryotherapy to the lesion. This will be performed on an outpatient basis.

The technique for local anesthesia will be 1% Lidocaine for the initial skin injection with 1% Lidocaine with Epinephrine (1:1000) for deeper injections. This will minimize bleeding and increase the duration of the Lidocaine. A 3.0-4.0 cm wide path of local anesthesia for each probe will be created by angulating the injection in several directions all the way to the tumor site. Intercostal nerve blocks will be achieved as needed with Lidocaine on each side of the lesions and on both sides of the affected rib.

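### The SUV formula in 7.0 as printed is 1,000 times off scale, and the staging sentences in 5.0 are not reconciled with Cohort B's target lung lesions

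*Combined protocol and SAP*

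**What the plan says.** **SUV definition.** Section 7.0 states that "Standard Uptake Value is calculated by the following formula". The numerator is the activity concentration in the region of interest, in µCi/ml. The denominator is the injected dose in µCi over the patient's weight in kilograms ("body weight (kg"). No kg-to-g conversion and no second definition of SUV appears anywhere. Section 9.3 plans point and interval estimates of SUVmean and SUVmax.

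**SUV limit.** Section 5.0 sets the limit: "There will be no areas that have SUV of greater than 2.5 in any location other than a primary lesion considered under control", the exemption being confined to the metastatic subgroup. It states no unit for 2.5. The sentence before it permits significant uptake only in the primary lung lesion.

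**Who the staging paragraph covers.** The first paragraph of 5.0 opens with patients who have Stage I primary lung cancer or limited metastatic disease, so it takes in both cohorts. It then says: "All patients will have no evidence of cerebral disease, no evidence of metastatic disease by the PET scan or the CT scan". It also rules out satellite lesions on chest CT.

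**What Cohort B is.** Section 2.0 defines it as patients with "metastatic solitary or multiple (≤ 3) peripheral lung lesions" under 3.0 cm. Section 4.1 items 3 and 9 allow up to three such lesions, with the lung as the only metastatic site. The second paragraph of 5.0, on metastatic patients, also accepts up to three lesions and asks that imaging show no *other* metastatic disease.

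**The concern.** There are two separate slips.

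First, the printed units do not give an SUV on the scale where a limit of 2.5 has meaning. If the values were computed from the printed line, a named secondary summary would be reported on the wrong scale, and the limit in 5.0 would screen nobody out.

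Second, the all-patient sentences and the SUV exemption in 5.0 do not mention the metastatic lung lesions that Cohort B is enrolled to have treated. A coordinator who applies the first paragraph literally reaches a different answer on a Cohort B patient from one who applies 4.1. With only 10 evaluable patients, the document should give one answer.

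**Working it through.** **Part 1: units.** The plan gives no worked SUV to reproduce, so the check is dimensional, with one reference case.

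Inputs from the documents: concentration C in µCi/ml, dose D in µCi, weight W in kg (7.0); limit 2.5 (5.0); maximum lesion diameter 3.0 cm (2.0, 4.1). Assumptions, not in the documents: body density about 1 g/ml; weight 50 to 100 kg; dose 10,000 µCi for illustration (it cancels).

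- Natural reading: SUV = C ÷ (D/W). Units: (µCi/ml) ÷ (µCi/kg) = kg/ml.
- Evenly spread tracer, 70 kg: C = 10,000/70,000 = 0.1429 µCi/ml; D/W = 10,000/70 = 142.9 µCi/kg; SUV = 0.1429/142.9 = 0.001.
- Same case with W in grams: D/W = 10,000/70,000 = 0.1429 µCi/g; SUV = 1.0 g/ml. The ratio is 1,000. Dose and weight both cancel, so it is the same for every patient. Densities of 0.95 to 1.05 g/ml give 0.95 to 1.05 in grams and 0.00095 to 0.00105 as printed; the ratio does not change.
- Same case with D in mCi and W in kg: 1 mCi/kg = 1,000 µCi/1,000 g = 1 µCi/g, so the result is again in g/ml. Either edit repairs the formula.
- A lesion at 2.5 on the gram scale reads 0.0025 as printed. To read 2.5 as printed it needs 2.5/0.001 = 2,500 times the body-average concentration, which is a fraction 2.5/W of the injected dose in each ml (W in kg).
- A 3.0 cm sphere has volume (4/3)π(1.5)³ = 14.1 ml. The share of the whole injected dose it would have to hold is 14.14 × 2.5/W:

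| Weight | Share of dose in one 3.0 cm lesion |
|---|---|
| 50 kg | 71% |
| 70 kg | 50% |
| 100 kg | 35% |

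- Strict left-to-right reading, (C/D)/W: even spread gives 1/(1,000 × W²), which at 70 kg is 1/4,900,000 (1/2,500,000 at 50 kg and 1/10,000,000 at 100 kg). This reading is further off, so it does not rescue the line.

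That 2.5 is meant on the gram scale is an inference: the documents give it no unit, but on the kg scale it cannot work.

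**Part 2: wording of 5.0 against the cohort definitions.** No arithmetic applies.

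| Rule in the first paragraph of 5.0 | Effect on a Cohort B target lesion | Text pointing the other way |
|---|---|---|
| No metastatic disease on PET or CT, all patients | The target is itself metastatic disease | 2.0; 4.1 items 3 and 9; Cohort B paragraph of 5.0 |
| No satellite lesions on chest CT | Not stated whether a second or third target counts; the term is undefined | 2.0 and 4.1 item 3 (up to three lesions) |
| Significant uptake only in the primary lung lesion | Fits Cohort A; a Cohort B target is not a primary lung lesion | Cohort B paragraph of 5.0 |
| SUV limit 2.5, exempting only a controlled primary | Not exempted | None that addresses SUV |

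The first three rows conflict with, or are left unclear by, text elsewhere. In the fourth the document is silent: nothing says whether the limit applies to the target metastases.

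**The case against.** The strongest case on the other side has five parts.

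- **The fault may not be the authors'.** The text was machine-read from PDF. If the source gives the dose in mCi, the formula is right with weight in kg, and one misread character would produce exactly this factor. This cannot be settled from the text available, so the source must be checked before anything is edited.
- **Nobody may compute SUV by hand.** Section 7.0 assigns the PET scans to a designated reader, and 5.0 does not refer to the formula. A reader might infer that the PET staging rule is disabled in operation. The documents do not support that; they show only that the printed definition, if followed, would not work.
- **The intent for Cohort B is visible.** The word *other* in 5.0's Cohort B paragraph, and items 3 and 9 of 4.1, accept the target metastases. A reader might infer from the first paragraph that Cohort B is shut out altogether. Read as a whole, the document does not say that. What stands is an unreconciled conflict, plus an SUV exemption that does not mention these lesions.
- **The limit is not a listed criterion.** Sections 4.1 and 4.2 contain no SUV limit; 4.1 item 7 asks only for baseline CT and PET. The figure 2.5 appears only in the narrative of 5.0. This stands, and it lowers the weight of the point.
- **The analysis barely moves.** Section 9.3 plans summaries of SUV, with no threshold or test. A constant factor rescales means and intervals and changes no inference. This also stands.

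**Conclusion.** Both slips are real as written, and both are minor.

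The 1,000-fold factor is exact under the natural reading of 7.0. Density of about 1 g/ml is assumed only to say what an evenly spread tracer would read. Taken literally, the SUV summaries in 9.3 come out 1,000 times too small and the 2.5 limit cannot be exceeded in practice. Separately, the first paragraph of 5.0 conflicts with its own Cohort B paragraph, with 2.0 and with 4.1.

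It is tempting to read the two as errors that compound, or that pull eligibility in opposite directions. On the SUV limit they cannot act together: with the printed formula nothing exceeds 2.5, so the missing exemption matters only once the units are right. The conflict over metastatic disease exists whatever the units.

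The primary endpoint, the 10 evaluable patients and the precision table in 9.2 are unaffected. Section 9.2 expects most or all patients to be in Cohort A, which further limits the reach of the second slip.

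**What to change.** 1. In 7.0, check the formula against the source PDF. If it is printed there as read here, correct the units so that SUV is in g/ml: either body weight in grams with dose in µCi, or dose in mCi with weight in kg. State that the 2.5 in 5.0 and the summaries in 9.3 are on that scale.
2. In 5.0, reconcile the sentences on metastatic disease, satellite lesions, permitted uptake and the SUV limit with the Cohort B paragraph in the same section, with 2.0 and with 4.1 items 3 and 9. The document should say once, and consistently, how each applies to Cohort B's target lung lesions. Which staging rule to adopt is for the investigators; this review does not propose one.

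The cost is a few wording edits. No scan, endpoint, sample size or analysis method changes. If the PET values reported to the study are already in g/ml, which the documents do not say, no recorded value changes either.

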7.1 Measurement of effect

Size of a lesion is defined as diameter in at least one dimension on chest x-ray or CT. The lesion would be a maximum of 3.0 cm or less by chest x-ray or X-ray.

7.2 Response Criteria

Complete response – CR disappearance of the entire target lesion.

Partial response – PR at least 30% decrease in the longest diameter of the target lesion using as a reference the baseline diameter.

7.3 Pathological Response

The tumor will be evaluated by a pathologist, [name] [contact]) in the Harper University Hospital , DMC/Wayne State University Pathology Department. The entire resected specimen and the lymph nodes will be re-evaluated for presence of tumor. In addition, the remainder of the treated lung will be analyzed for response to cryotherapy, including damage to lung parenchyma, connective tissue and blood vessel. Any area of hemorrhage will be noted.

7.4 Follow-Up

All patients who are registered to the trial will be followed for survival regardless of whether the patient completed protocol treatment.

[figure not shown]
[figure not shown]
All adverse events and serious adverse events that are related to protocol treatment will be followed until resolution.

7.5 Evaluable patients.

To be evaluable for this pilot study, the patient must undergo the planned thoracotomy < 12 weeks from percutaneous cryotherapy, as noted in the Study Calendar. Inevaluable patients will be replaced until the statistically required sample size of 10 evaluable patients (as determined in Section 9.2) has been obtained.

8.0 **Figure 1: The 1-2 rule for cryoprobe placements according to tumor size (black circles)**

Using a single cryoprobe requires precise central placement [22] to cover the tumor with ice (darker gray around each probe), let alone lethal ice (smaller dashed line ~5 mm inside ice). Conversely, when more probes are used, the sum of the individual ice projections (darker gray circles) synergistically expand, extending lethal ice (larger dashed line) ~ 5 mm beyond all tumor margins while visible ice (lighter gray circle) projects ~ 10 mm.

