1.0 SCHEMA

Prior to lung resection at three weeks after PTC, the patient will receive a dynamic enhanced (i.e., non-contrast, arterial and delayed phase) computed tomography(CT) of the chest. These preoperative studies will be compared with the histologic results from thoracotomy, obtained at least 2 days after PTC and no more than 2 months after PTC to assure thorough necrosis. Evaluations will include dimensions of the resected pathologic specimen's necrotic center and its peripheral rim, compared to the CT findings of vessel proximity, central cavitation and associated healing rim, noting the enhancement of the rim and overall ablation zone. The resected ablation zone will undergo histologic analyses of the tumor region near vasculature, as well as the anterior, posterior, superior, inferior, medial and lateral margins to determine if cancer is present and note the characteristics of the healing rim (e.g., inflammatory infiltrates). If cancer is present in any area, this will be compared to the similar ablation margin on CT to assess any differences in enhancement or nodularity.

Key Inclusion Criteria

1. The patient will be a candidate for a thoracotomy
2. The patient will have a peripheral lung tumor 3.0 cm or less in diameter
3. If primary lung cancer, non-invasive staging or mediastinoscopy will suggest the patient has Stage I disease. If patient has metastatic disease, the lungs will be the only site of metastases.
4. The patient will have a biopsy proven cancer before PTC and thoracotomy, including either a CT-guided needle biopsy diagnosis, a bronchoscopic or transbronchial biopsy.

Treatment Plan

1. The patient will undergo CT-guided PTC with the intent to eradicate the entire tumor(s).
3. The patient will have CXR at weeks 1 and 2 (± 2 days).
4. Approximately 3 weeks after PTC, (2-53 days) chest CT and pulmonary function tests will be performed within 7 days of planned resection.
5. Approximately 3 weeks after PTC (2-60 days) the patient will undergo a thoracotomy with resection of the treated lung, consisting of lobectomy for primary lung cancer or wedge resection with adequate margin for a metastatic lesion. The mediastinal lymph nodes will undergo dissection.
6. The resected ablation zone(s) will be measured and histologic samples taken from all six margins and resected lymph nodes.
7. The pathology results will be compared with the preoperative, post-cryotherapy CTs.

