There are no studies on the efficacy of percutaneous cryotherapy of lung tumors other than chest CT scan or by utilizing PET scan to demonstrate that no residual tumor is present.³⁷ There is no study that histologically demonstrates that the percutaneous cryoablation technique has been able to kill all viable tumor cells, including the potentially misleading breast cancer data which reports insufficient ablation of tumors >1.5 cm but only used 1 probe in all cases³⁸.

This study would resect the ablated lung tissue after a sufficient period of time to assure thorough necrosis by standard hematoxylin and eosin stains (i.e., >1 day), but not so long after cryotherapy that central necrosis can not be differentiated from healing rim (i.e., <60 days). This allows greater flexibility in the recruitment of patients surrounding their scheduled resection. The resected ablation zone will be measured to compare the average diameter in three dimensions with the CT scan dimensions. The diameter of the necrotic tumor and the ablated zone will be measured and compared with these areas on the CT scan. The ablative zone's regions of enhancement or nodularity (i.e., possible residual cancer) will be compared with regions (anterior, posterior, superior, inferior, medial and lateral) from the pathologic analysis of the tumor, including effects upon any adjacent bronchi and vasculature. We expect that all tumor will be eradicated with cryotherapy, but would define success as more than 75% of analyzed tissue being negative for cancer. Radiofrequency ablation frequently leaves residual tumor and recurrence rates range from 12-58%²²⁻²⁴ depending on tumor size and vessel proximity. Our hope is that the percutaneous cryoablation technique will show more thorough destruction of cancer cells.

The usual clinical scenario is that the patient who is receiving percutaneous cryotherapy does not have an operation or cannot have an operation. This study would give us the unique opportunity to resect the tissue, which has received cryotherapy, and determine whether this is a viable treatment option as a primary treatment modality rather than as a last ditch treatment, or treatment of last resort.

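### Study Calendar footnote J and Section 7.5 admit thoracotomy up to day 83 after cryotherapy, past the 60-day limit that the Schema and Section 3.4 set so that necrosis and healing rim stay distinguishable

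*Combined protocol and SAP*

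**What the plan says.** The protocol times the thoracotomy in several places.

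- **Schema, Treatment Plan item 5:** "Approximately 3 weeks after PTC (2-60 days) the patient will undergo a thoracotomy with resection of the treated lung". The Schema's opening paragraph says of the histology that it is "obtained at least 2 days after PTC and no more than 2 months after PTC to assure thorough necrosis".
- **Section 3.4** gives the scientific reason for an upper limit. Resection should be "not so long after cryotherapy that central necrosis can not be differentiated from healing rim (i.e., <60 days". The same paragraph plans the measurements that depend on that distinction: "The diameter of the necrotic tumor and the ablated zone will be measured and compared with these areas on the CT scan".
- **Study Calendar, footnote J** (Thoracotomy column): "Less than 12 weeks from percutaneous cryotherapy".
- **Section 7.5** makes that limit the test of evaluability: "the patient must undergo the planned thoracotomy < 12 weeks from percutaneous cryotherapy, as noted in the Study Calendar". Section 9.2 takes its 10 evaluable patients from 7.5.
- **Study Calendar, footnote I** (CT and pulmonary function tests): "2-53 days following percutaneous cryotherapy; within 7 days of planned thoracotomy". Schema item 4 gives the same day range and says that "chest CT and pulmonary function tests will be performed within 7 days of planned resection".

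Section 9.1 describes the primary tissue as examined three weeks after cryotherapy.

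**The concern.** One operation has two upper limits, and the looser one defines the analysis set. A patient resected between day 61 and day 83 is outside the Schema's treatment window. By Section 3.4, that patient's specimen is also too old for the necrotic centre to be separated from the rim. Yet the patient is evaluable and fills one of the ten places.

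At stake is the part of the secondary objective in Section 2.0 that compares central necrosis and healing rim on the pre-surgical CT with the same areas of the specimen. A late specimen can enter that comparison with no rule to mark it as one that the protocol's own rationale treats as unreadable for this purpose. With ten patients, each such pair matters to what can be learned about reading post-ablation CT.

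**Working it through.** **1. The limits in days.** Under 12 weeks is under 12 × 7 = 84 days, so the last allowed day is 83. The Schema's last day is 60. The difference is 83 − 60 = 23 days (days 61-83). Section 3.4, read strictly, ends at day 59, one day before the Schema; that difference is immaterial. Footnote J also has no lower limit, whereas the Schema starts at day 2.

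**2. Footnote I against footnote J.** For surgery planned on day D, the CT must fall in the overlap of [D − 7, D] and [2, 53].

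| Planned surgery day | CT days within 7 days before surgery | CT days also within 2-53 |
|---|---|---|
| 59 | 52-59 | 52-53 |
| 60 | 53-60 | 53 only |
| 61 | 54-61 | none (earliest is 1 day late) |
| 83 | 76-83 | none (earliest is 23 days late) |

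The latest plannable day under footnote I is 53 + 7 = 60, exactly the Schema's limit. Footnote I therefore fits the 60-day window and not footnote J.

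**3. Surgery that slips.** Footnote I refers to planned surgery, so a patient planned for day 60 with a CT on day 53 complies even if the operation is then delayed. For resection on day 61 the most recent in-window CT is at least 61 − 53 = 8 days old. For day 83 it is at least 83 − 53 = 30 days old.

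**4. Any reconciling text?** None was found. The remark in 3.4 about flexibility in recruitment refers to its own window of more than 1 and fewer than 60 days, not to 12 weeks.

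**5. The primary precision.** The only design figures that use the 7.5 set are those in Section 9.2, and both reproduce. The Wilson 80% half-width is z/(1 + z²/n) × √(p(1 − p)/n + z²/(4n²)). With z = 1.2816, n = 10 and p = 0.5, this is 1.1008 × √(0.025 + 0.0041) = 0.188, as stated. For the mean, t(0.90, 9 df)/√10 = 1.383/3.162 = 0.437 SD, as stated. Both depend on having ten evaluable patients, not on the day of resection, so the discrepancy leaves them unchanged.

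**6. The secondary comparison.** If k of the 10 are resected after day 60, the necrosis and rim comparison has 10 − k readable pairs. The documents give no basis for k.

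**The case against.** The strongest defence has three parts.

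First, an evaluability limit wider than the treatment window is ordinary and sensible. It avoids discarding a patient who has had both cryotherapy and resection. This stands, and the fix keeps 12 weeks in 7.5. However, the protocol never says that this is the intent. Footnote J is the calendar's only thoracotomy window rather than an analysis rule, and 7.5 simply points back to it.

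Second, a reader might infer that a site following the calendar is free to plan surgery for days 61-83. That goes too far. Footnote I belongs to the same calendar, and a site that obeys both footnotes cannot plan past day 60. The exposure is therefore mainly surgery that slips, or footnote J read alone. The missing CT window is a symptom of the same mismatch and not a second error.

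Third, the impact is small. Section 2.0 calls the comparison qualitative, and Section 9.3 expects that the histologic assessment will not need statistics. Accrual is about two patients a year, with monthly team review. This too stands and limits the weight of the point. It does not remove the conflict: a written rule admits specimens that the rationale says cannot support a planned measurement.

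**Conclusion.** The conflict is real and unreconciled: day 83 against day 60, a gap of 23 days, with footnote J also at odds with footnote I. It is worth correcting because the correction is nearly free, but its reach is narrow. It touches the necrotic-centre and healing-rim measurements and their comparison with CT. How many patients this involves is unknown and may be zero, since surgery is aimed at about three weeks.

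Two stronger readings are tempting. One is that late resection biases p or mean % TNC. The documents do not support it: Section 3.4 speaks of telling necrosis from rim, and nowhere does the protocol say that residual cancer becomes undetectable after day 60. The other is that the stated precision is wrong. It is not, because N stays at 10. For the same reason, nothing here justifies removing late specimens from the comparison of residual cancer by margin with CT.

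The conclusion assumes that Section 3.4's limit means what it says about distinguishing necrosis from rim, and that no unstated tolerance was intended to govern these measurements. Because Section 9.1 describes the tissue as three weeks old, the actual surgery days belong alongside p whatever the intent was.

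**What to change.** - **Footnote J:** change to 2-60 days after PTC. This matches the Schema and footnote I and supplies the missing lower limit.
- **Section 7.5:** state that a patient whose planned resection is delayed past day 60 but is done within 12 weeks of PTC remains evaluable for p and mean % TNC, and stop referring to the calendar for that limit.
- **Reporting:** list the actual CT and surgery days for every patient.
- **Necrosis and healing-rim measurements and their CT comparison:** restrict to specimens resected by day 60, and list later ones descriptively.
- **Residual cancer by margin against CT:** keep late specimens in, with the CT-to-surgery interval shown.

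The cost is a few lines of wording and one listing. Evaluability stays at 12 weeks, so no patient needs replacing and no extra enrolment follows. The downside is that the rim comparison may have fewer than 10 pairs if any resection is late.
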